1 STUDY SYNOPSIS

Title	Use of Cheetah® non-invasive cardiac monitoring system to guide discontinuation of postpartum magnesium sulfate in women with severe preeclampsia: A pilot randomized control trial.
Objective	Demonstrate the utility of using improvement in SVR via non-invasive cardiac monitor as an indicator for resolution of preeclampsia, and individualize the duration of magnesium in the postpartum period for women with preeclampsia with severe features.
Study Population	Pregnant women greater than 18 years of age and 24 0/7 weeks' gestational age admitted to L&D for delivery with preeclampsia with severe features and plan to receive magnesium sulfate.
Study Design	This is a single site pilot randomized, controlled, trial randomizing patients with PE with severe features to one of 2 groups: 
• 24 hours of postpartum magnesium sulfate (current arbitrary standard of care)• Using the Cheetah® device to aid in an individualized duration of magnesium sulfate based on reduction in SVR, up to a maximum of 24 hours postpartum.
Eligibility	Subjects enrolled in the RCT must meet all of the inclusion criteria listed below: Inclusion Criteria 
• PE with severe features, diagnosed using the ACOG standard criteria⁴ requiring magnesium sulfate• Females older than 18 years of age• Singleton pregnancy• Gestational age greater than 24 0/7 weeks• The patient is physically and mentally able to understand the informed consent and is willing to participate in this study• Able to speak English or Spanish Subjects enrolled in the RCT must not have any of the exclusion criteria listed below: Exclusion Criteria 
• Multiple gestation• Prisoners• Patients with chronic renal insufficiency or epilepsy• Known cardiovascular disease• Patients with contraindications to magnesium sulfate use (e.g. myasthenia gravis)

Clinical Protocol: Cheetah® OSU study

	
• Patients with eclampsia or HELLP syndrome• Contraindications for magnesium sulfate 
(In addition to subjects enrolled in the RCT, we propose an optional negative control cohort of 25 normotensive healthy women delivering > 37 weeks to compare hemodynamics)

Site	The Ohio State University Wexner Medical Center
Sample Size	60 patients with preeclampsia with severe features and plan to receive magnesium sulfate. (In addition to subjects enrolled in the RCT, we propose an optional negative control cohort of 25 normotensive healthy women delivering > 37 weeks to compare hemodynamics)
Study Duration	Estimated duration of study is approximately 1 year.

Clinical Protocol: Cheetah® OSU study

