Moreover, there is no consensus in the published trials regarding the optimal dose to use (both loading and maintenance), or the duration of therapy (especially in the postpartum period) ⁴. Multiple recent studies have questioned the utility of the use of magnesium sulfate for 24 hours postpartum and suggest no increased risk of eclampsia or maternal morbidity with use of shorter durations of use (such as 6 hours or 12 hours)¹²⁻¹⁴. However, most studies have no clear definition of a clinical parameter that defines the recovery phase from severe PE. One of several parameters that has been described as an indicator of clinical improvement from PE is the onset of diuresis¹⁵. This is believed to be a signal for reversal of increased SVR (vasoconstriction), and thus resolution of the disease. Historically, it was only possible to measure SVR with an invasive monitor such as a pulmonary artery catheter. The potential complications with these measurements outweighed the risk of benefit. Novel techniques including thoracic bioreactance, enable minimally invasive measurements of SVR and have been validated in the obstetric population.¹⁶

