3.3 SVR as a measure of disease resolution

Although, the use of MgSO₄ is to prevent eclamptic seizures, the rarity of these events in the U.S. severely diminishes the feasibility of any research study with seizure mitigation as a primary outcome. **Therefore, a hemodynamic surrogate end point (SVR), based on the key mechanism of action of MgSO₄ as a vasodilator for eclampsia prevention, was selected.**

We are proposing to measure improvement in SVR using a novel, non-invasive, and well-validated hemodynamics monitoring system, as a criterion to discontinue MgSO₄, in the postpartum period. Although the exact etiology of eclampsia is still unknown, it is believed that cerebral vasospasm plays an essential role. It is hypothesized that in the setting of PE, and as blood pressure increases out of the normal range, cerebral resistance increases to limit cerebral perfusion. Ultimately, with increasing blood pressure and cerebral perfusion pressure, autoregulation is lost, which in the setting of endothelial dysfunction leads to vasogenic edema, overperfusion injury, and eclampsia. Magnesium is a calcium antagonist and can act on many calcium channels in the vascular smooth muscle. This leads to decrease in intracellular [Mg²⁺], inactivation of calmodulin-dependent myosin light chain kinase activity and reduced vascular tone, which subsequently leads to vascular (arterial) relaxation, and dilatation. Since vascular resistance is inversely related to the 4th power of blood vessel radius, effect of MgSO₄ on vasodilation has the most significant impact on peripheral and cerebral vascular resistance. This vasodilatory effect of MgSO₄, which we can detect peripherally, using Cheetah non-invasive cardiac monitoring, severs as a rationale for this study.

Clinical Protocol: Cheetah® OSU study

Therefore, we sought to demonstrate the utility of using improvement in SVR via non-invasive cardiac monitor as an indicator for resolution of PE, and individualize the duration of magnesium in the postpartum period for women with PE with severe features.

4 Hypothesis

We hypothesize that the use of the Cheetah® non-invasive cardiac monitor to individually determine the duration of magnesium sulfate postpartum (guided by timing of reduction in SVR) will result in shorter duration of MgSO4 infusion, compared with the traditional preset time point of 24hr postpartum, with no increase in maternal morbidity.

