5 STUDY DESIGN

5.1 Type of Study

This is a single site pilot randomized, controlled, trial randomizing patients with PE with severe features to one of 2 groups:

- 24 hours of postpartum magnesium sulfate (current arbitrary standard of care)
- Using the Cheetah® device to aid in an individualized duration of magnesium sulfate based on reduction in SVR, up to a maximum of 24 hours postpartum.

A 30% reduction in SVR (maintained for 1 hour) from the time of delivery will be used as an indicator for resolution of PE and as the cutoff for discontinuation of magnesium sulfate. This SVR reduction is previously described in normal pregnancy within 1 hour postpartum² and similar reduction in SVR in pregnancies complicated by severe PE, from after delivery to 24-36hrs postpartum⁶.

In addition to subjects enrolled in the RCT, we propose an optional negative control cohort of 25 normotensive healthy women delivering > 37 weeks to compare hemodynamics.

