5.3 Study Outcomes

Primary Outcome:

Duration of magnesium sulfate use in the postpartum period defined as the duration in hours between delivery and discontinuation of magnesium sulfate.

Secondary safety Outcome:

Composite of eclampsia, pulmonary edema, renal insufficiency/acute kidney injury, venous thromboembolism, peripartum cardiomyopathy, ICU admission, or maternal death.

Secondary Maternal clinical Outcomes

Maternal secondary outcomes

- Need for or up-titration of antihypertensive agents postpartum for severe hypertension
- Hospital readmission up to 4 weeks postpartum
- Changes in arterial blood pressure in the peripartum period
- Changes in cardiac output during the peripartum period
- Changes in heart rate in the peripartum period
- Need to restart magnesium sulfate
- Urine output, and the onset of diuresis defined as UOP >0.5ml/hour for 2 consecutive hours
- Preeclampsia symptoms resolution
- Correlation between magnesium levels and changes patient hemodynamics
- Anesthetic type
- Length of stay in Labor and delivery
- Total hospital length of stay
- Hospital cost
- Patient satisfaction

Clinical Protocol: Cheetah® OSU study

- Time to start regular diet and ambulation
- Maternal non-invasive cardiac parameters pre- and post-neuraxial anesthesia, pre- and post starting magnesium sulfate, with pushing or during cesarean delivery, and after the use of different anti-hypertensives (e.g. labetalol, nifedipine, hydralazine) for emergent therapy for severe hypertension
- Postpartum hemorrhage or blood transfusion
- Postpartum resources utilization including ER/triage visits, scheduled or non-scheduled clinic visits

Neonatal secondary outcomes

- Fetal or neonatal death
- Intubation, continuous positive airway pressure (CPAP) or high-flow nasal cannula (HFNC) for ventilation or cardiopulmonary resuscitation within first 72 hours
- Composite of either neonatal encephalopathy as defined by the NICHD Neonatal Research Network criteria, seizures, or intracranial hemorrhage (intraventricular hemorrhage, subgaleal hematoma, subdural hematoma, or subarachnoid hematoma)
- Hyperbilirubinemia requiring phototherapy or exchange transfusion
- Hypoglycemia (glucose < 35 mg/dl) requiring IV therapy
- NICU admission and length of stay in NICU

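### No listed outcome or planned analysis assesses whether the SVR criterion indicates resolution of preeclampsia, and the primary outcome cannot stand in for that half of the objective

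*Combined protocol and SAP*

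**What the plan says.** The objective (section 1, repeated at the end of section 3.3) has two halves. The first is to "Demonstrate the utility of using improvement in SVR via non-invasive cardiac monitor as an indicator for resolution of preeclampsia". The second is to individualize how long magnesium runs after delivery. The hypothesis (section 4) concerns only duration and safety: the device-guided approach "will result in shorter duration of MgSO4 infusion, compared with the traditional preset time point of 24hr postpartum, with no increase in maternal morbidity".

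Section 5.1 takes the indicator as given: "A 30% reduction in SVR (maintained for 1 hour) from the time of delivery will be used as an indicator for resolution of PE". The same fall is the stop rule in the Cheetah arm, "up to a maximum of 24 hours postpartum". Control receives 24 hours.

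The primary outcome (sections 5.3 and 7.2.1) is hours from delivery to stopping magnesium. The secondary list includes "Changes in cardiac output during the peripartum period", with similar lines for blood pressure and heart rate. It also has urine output with onset of diuresis and, separately, "Preeclampsia symptoms resolution". The broader line on non-invasive cardiac parameters is tied to neuraxial anesthesia, magnesium start, pushing or cesarean, and antihypertensives. The only association listed is between magnesium levels and hemodynamics. Section 7.2.4 makes everything beyond the primary efficacy analysis exploratory.

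Of diuresis, section 3.2 says: "This is believed to be a signal for reversal of increased SVR (vasoconstriction), and thus resolution of the disease".

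**The concern.** SVR drives the intervention, yet its postpartum course is not a listed outcome. Nor are the share of women meeting the 30% criterion, the time they meet it, or its relation to any sign of recovery. Section 3.2 criticizes earlier studies for lacking a clear parameter of recovery and names diuresis as one candidate, but the plan never sets SVR against it.

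If the plan is followed exactly, the report will say how long magnesium ran. It will not say whether the SVR fall came before, with or after diuresis or symptom resolution. A shorter duration could then be read as validating SVR as a marker of resolution, and a later trial could be built on that reading.

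**Working it through.** **1. Objective against outcomes.**
- Individualized duration: addressed by the primary outcome.
- SVR as indicator: needs the criterion compared with something that represents resolution. Two candidates are listed in section 5.3 (diuresis onset, symptom resolution). Neither is paired with SVR there or in sections 7.2.1 to 7.2.5.

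**2. The plan's own figure.** No sample size or precision is given for the indicator question. The only size is 21 per arm for a 4 h difference (section 7.2.5; two-sided 5%, 90% power). From n = 2(z₀.₉₇₅ + z₀.₉₀)²SD²/Δ², the unstated SD is 4 / [(1.960 + 1.282) × √(2/21)] ≈ 4.0 h. I use 21 per arm below only as the planned evaluable size.

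**3. Can the primary result support the indicator claim?** Assumptions: control stops at exactly 24 h, and Cheetah stop times are random and unrelated to resolution. There were 2,000 simulated trials per scenario at 21 per arm, tested two-sided at 5% with the two tests named in section 7.2.4:

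| Cheetah stop time | Mean (h) | t-test significant | Wilcoxon significant |
|---|---|---|---|
| Uniform 0–24 h | 12.0 | 100% | 100% |
| Uniform 12–24 h | 18.0 | 100% | 100% |
| Half never meet criterion (24 h), rest uniform 1–24 h | 18.2 | 99.2% | 99.95% |

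The adjusted regression was not simulated. The result needs the rule to fire in a fair share of women, and these scenarios shorten the mean by about 6 to 12 h. They show that significance depends on how often and how early the rule fires, not on whether it marks resolution.

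**4. Is the timing of the criterion known?** Section 5.1 cites a fall within 1 h in normal pregnancy; with the 1 h hold, the criterion is met by about 1 + 1 = 2 h. It also cites a "similar reduction in SVR in pregnancies complicated by severe PE, from after delivery to 24-36hrs postpartum". Under a 24 h cap with a 1 h hold, the fall must be present by 24 − 1 = 23 h. The second citation gives the period over which a reduction was described, not when 30% was first reached. The share meeting the criterion before the cap is therefore open.

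**5. Precision of the missing analysis.** For a proportion near 0.5, the 95% half-width is 1.96√(0.25/n). I assume 1:1 allocation of 60.
- n = 30: 1.96 × √0.00833 = 0.179, about 18 points.
- n = 25 (30 × 0.85 = 25.5, the plan's 15% dropout): 1.96 × 0.10 = 0.196, about 20 points.
- Exact intervals for 80% agreement: 24/30 gives 0.61 to 0.92; 20/25 gives 0.59 to 0.93.
- Symptom resolution applies only to women with symptoms at baseline, a number the documents do not give. If it were 15, the half-width would be 1.96 × √(0.25/15) = 0.253, about 25 points.

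**The case against.** A reader might infer that the trial cannot answer the indicator question, or that a positive result says nothing about the objective. The documents do not support either reading. The objective's second half is addressed directly, and the hypothesis in section 4 matches the primary outcome and the safety composite. Need to restart magnesium and antihypertensive up-titration bear indirectly on utility. Section 5.4 collects cardiac parameters and hourly urine output, so the comparison could be made afterwards in the Cheetah arm.

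A reader might also infer that only time-to-criterion data would show whether the rule fires early. That is too strong. The criterion is the stop rule, so Cheetah-arm duration already approximates time to criterion capped at 24 h, apart from stops for other reasons.

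Hours-saved projections can be built, but they need inputs found nowhere in the documents. A linear fall averaging 30% at 30 h, with a between-woman SD of 6 to 15 points, gives 0.1 to 1.1 h saved. An early fall with a time constant of 3 to 6 h gives about 5 to 9 h. These are scenarios, not predictions.

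These objections narrow the point but do not remove it. Duration carries no information on agreement with a resolution marker. The safety composite is weak support at this size: 0 events in 30 leaves a one-sided 95% upper bound of 1 − 0.05^(1/30) = 9.5%. A comparison chosen after the data are seen is a poor basis for the first-named objective, even in a pilot.

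**Conclusion.** The point holds in this form: as planned, the trial does not assess whether the SVR criterion indicates resolution, and a positive primary result would not be evidence that it does. This rests on the outcome list and section 7.2 as written, and on control duration being close to 24 h. The gap lies in what is prespecified, not in what the design could collect. The question can be estimated in the Cheetah arm with modest precision, about ±18 to ±20 points for 30 to 25 evaluable women under 1:1 allocation. That is reasonable for a pilot.

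**What to change.** Add two named exploratory secondary outcomes in the Cheetah arm.

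(a) The proportion meeting the SVR criterion before 24 h, and time from delivery to criterion by Kaplan-Meier. Record the reason for every stop, so that stops driven by the criterion, the cap and other causes are reported separately.

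(b) The order and timing of the criterion relative to diuresis onset and, in women with symptoms at baseline, symptom resolution. Report the proportion in whom the criterion came first, with its 95% CI. Treat women who do not reach the criterion or the marker by 24 h as censored; do not drop them from a median difference. Report separately those who reach neither.

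State that any conclusion about SVR as an indicator of resolution rests on (b), not on the primary outcome.

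The cost is protocol wording, a small analysis and some data-collection detail; randomization and sample size are unchanged. Matters to settle or state:
- The diuresis definition in section 5.3 (above 0.5 ml/hour for two hours) must be reconciled first. As written, almost any urine output meets it, which would make the comparison uninformative.
- The clock time of symptom resolution may need a CRF field, and no end time is given for hourly urine output.
- Device placement is stated only for the Cheetah arm, so it is unclear whether SVR is recorded in controls.
- Markers that occur after the criterion are observed after magnesium has stopped, which limits interpretation of (b).

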2 LIST OF ABBREVIATIONS

ACOG	American Congress of Obstetricians and Gynecologists
BMI	Body Mass Index
BP	Blood Pressure
CFR	Code of Federal Regulations
CI	Confidence Interval
CO	Cardiac Output
CRF	Case Report Form
GCP	Good Clinical Practice
HELLP	Hemolysis, Elevated Liver Enzymes, Low Platelet Count
HIPAA	Health Information Portability and Accountability Act
HR	Heart Rate
ICF	Informed Consent Form
IDE	Investigational Device Exemption
IRB	Institutional Review Board
IV	Intravenous
LMP	Last Menstrual Period
MAP	Mean Arterial Pressure
Mg ²⁺	Magnesium Ion
MgSO ₄	Magnesium sulfate
NICU	Neonatal intensive care unit
PE	Preeclampsia
SAE	Serious Adverse Event
SD	Standard deviation
SVR	Systemic Vascular Resistance

Clinical Protocol: Cheetah® OSU study

3 BACKGROUND

3.1 Pregnancy hemodynamic changes

Pregnancy is a dynamic process associated with significant physiological changes in the cardiovascular system. These changes include an increase in cardiac output (CO), heart rate (HR), blood volume expansion, and a decrease in blood pressure (BP) and systemic vascular resistance (SVR) during pregnancy¹. On the other hand, labor is associated with significant hemodynamic changes, including increased CO and BP, and other parameters which are altered after administration of neuraxial anesthesia^{2,3}. Additionally, after the delivery of the placenta, there is a rapid return of CO and SVR to non-pregnant levels².

3.2 Preeclampsia

Preeclampsia (PE) is a multisystem disorder affecting up to 8% of pregnancies and is diagnosed using standard clinical and biochemical criteria (Box 1)⁴. PE with severe features is diagnosed with either systolic blood pressure of 160mm Hg or more, or diastolic blood pressure of 110mm Hg or more on two occasions at least 4 hours apart (unless antihypertensive therapy is initiated before this time) and/or the presence of end organ injury such as thrombocytopenia, liver or renal injury, pulmonary edema, persistent symptoms (as defined in box 1) or eclampsia.

Globally, PE is a leading cause of morbidity and mortality for pregnant women. Pregnant women who develop PE are at risk of eclampsia, a serious complication defined as new onset seizures and/or unexplained coma in the setting of PE, stroke, placental abruption, coagulopathy, pulmonary edema, acute kidney injury, liver hematoma, intracranial bleeding, cardiopulmonary arrest, and death. Moreover, PE increases risk of future cardiovascular disease and represents a significant economic burden on healthcare systems⁵. Published literature has identified striking differences in the maternal hemodynamic profiles between normotensive pregnancies and those complicated by PE. **PE is associated with a significantly higher BP and SVR with lower HR, stroke volume, and CO⁶.**

Women with PE also have higher levels of placental-derived anti-angiogenic proteins and significantly lower levels of pro-angiogenic proteins, when compared with healthy pregnant women⁷. The increased SVR noted in pregnancies complicated by PE have been associated with abnormal plasma levels of angiogenic proteins^{7,8}.

The cure for PE has remained the same for several decades: delivery of the fetus and placenta. Immediately after birth, there is resolution of many of the clinical symptoms of PE, including a decrease or normalization in BP, improvement in urine output, and improvement of symptoms of end organ damage, along with reduction in stroke volume, CO, mean arterial pressure (MAP), and SVR⁶.

In the U.S., parenteral magnesium sulfate (MgSO₄) is routinely given to pregnant women for the prevention of eclampsia in patients with PE, especially those with severe features, as multiple

Box 1: Criteria for Diagnosis of PE
Systolic blood pressure of 140mm Hg or more, or diastolic blood pressure of 90mm Hg or more on two occasions at least 4 hours apart (unless antihypertensive therapy is initiated before this time)

AND one of

- Proteinuria (urine protein/creatinine ratio >0.3, 24-hour urine protein \geq 300mg or \geq +2 proteinuria on urine dipstick)
- Thrombocytopenia (platelet count less than $100,000 \times 10^9/L$)
- Impaired liver function as indicated by abnormally elevated blood concentrations of liver enzymes (to twice the upper limit of normal concentration), and severe persistent right upper quadrant or epigastric pain unresponsive to medication and not accounted for by alternative diagnoses
- Renal insufficiency (serum creatinine concentration more than 1.1 mg/dL or a doubling of the serum creatinine concentration in the absence of other renal disease)
- Pulmonary edema
- New-onset headache unresponsive to medication and not accounted for by alternative diagnoses
- Visual disturbances

Clinical Protocol: Cheetah® OSU study

studies and meta-analyses demonstrated its superiority compared with other agents⁹. However, despite the clear and therapeutic importance of MgSO₄ in pregnancy, there are limited data on its optimal dosing. The MgSO₄ dosing regimen currently used is based on a protocol developed more than 30 years ago and does not take into account patient characteristics. In addition, the “therapeutic dose” of MgSO₄ has been determined empirically and is based upon historic dosages found to be typically tolerable and effective. In clinical practice, dosing is based on a standard protocol, irrespective of patient’s characteristics. Typically, it is administered by an intravenous (IV) infusion with a loading dose of 4 to 6 grams over 15-30 minutes, followed by 2 g/h as a continuous IV infusion up to 24 hours postpartum⁹. The use of MgSO₄ requires a higher level of care with frequent blood pressure monitoring, close urine output monitoring, and frequent examinations for signs of magnesium toxicity (such as loss of deep tendon reflexes and respiratory depression)¹⁰. It is estimated that women receiving MgSO₄ are almost 5 times more likely to experience adverse events compared with those receiving no or other treatments. This is associated with significant healthcare costs¹¹ and patients dissatisfaction.

Moreover, there is no consensus in the published trials regarding the optimal dose to use (both loading and maintenance), or the duration of therapy (especially in the postpartum period) ⁴. Multiple recent studies have questioned the utility of the use of magnesium sulfate for 24 hours postpartum and suggest no increased risk of eclampsia or maternal morbidity with use of shorter durations of use (such as 6 hours or 12 hours)¹²⁻¹⁴. However, most studies have no clear definition of a clinical parameter that defines the recovery phase from severe PE. One of several parameters that has been described as an indicator of clinical improvement from PE is the onset of diuresis¹⁵. This is believed to be a signal for reversal of increased SVR (vasoconstriction), and thus resolution of the disease. Historically, it was only possible to measure SVR with an invasive monitor such as a pulmonary artery catheter. The potential complications with these measurements outweighed the risk of benefit. Novel techniques including thoracic bioreactance, enable minimally invasive measurements of SVR and have been validated in the obstetric population.¹⁶

